During the initial phone recruitment interview, the PI will explain the nature of the study, risks, benefits, length, voluntary nature of participation, and the right to discontinue participation at any time without consequences and will screen potential participants for eligibility according to the inclusion and exclusion criteria. DR parents that are screened and meet eligibility requirements will be informed of the study website and provided the URL and a unique study code, which will serve as a portal for enrolling and providing demographic information and obtaining Informed Consent, completing the online Surveys and administering the TELL Tool or eBook interventions.

DR parents that are randomized to the TELL Tool **intervention group** will complete four online modules that are based on our prior research with DR parents. These four modules center on DR parents' cognitive, emotional, moral and relationship concerns that arise when DR parents consider whether to tell or not to tell their child(ren) about their donor-conception origins. The TELL Tool is designed using several strategies that enable DR parents to engage with the online materials. In addition, the TELL Tool is custom-tailored for DR parents by the type of family (for example a single-parent family versus a two-parent family), the type of donation (egg, sperm, or embryo) the DR parents used, and the age(s) of the DR parent's child or children. It will take DR parents about 60 minutes to complete the TELL Tool online modules. Immediate post-intervention DR parents will be directed to the post-test web page to complete (1) the *Outcomes Survey** measuring our (preliminary) outcomes for intention, competence, and anxiety about disclosing the donor conception to their children, and (2) the *Acceptability of the TELL Tool or eBook Survey.*** Then, at 4-weeks and 12-weeks post-intervention, DR parents will complete the *Survey on Actual Parental Disclosure.*

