The DR parents that are randomized to the **attention-control eBook group** will complete a 60-minute online program that has up-to-date information about strategies that promote good parenting skills. The eBook has graphics and photographs that make it visually engaging for DR parents and easy to use. Immediate post-attention control, DR parents will be directed to the post-test web page to complete the (1) *Outcomes Survey** measuring our (preliminary) outcomes for intention, competence, and anxiety about disclosing the donor conception to their children, and (2) the *Acceptability of the TELL Tool or eBook Survey.*** Then, at 4-weeks and 12-weeks post-attention control, DR parents will complete the *Survey on Actual Parental Disclosure.**** After all data are obtained, we will complete Year 1 analyses and make modifications to the TELL Tool, eBook, and protocols, as needed.

In Year 2 of the study, Cognitive Interviews will be conducted on a selected sub-sample of 10 DR parents and 10 practicing clinicians. Participants will be asked to complete individual interviews where they will be asked specific questions about how the TELL Tool and eBook and its design and administration can be improved further. We will use an Interview Guide, developed for the study that builds on our prior research and also uses guidelines and standards for developing decision aids to elicit information from DR parents and clinicians. In keeping with good scientific practice, the PI will use an Interviewer Summary Form to make field notes about observations when DR parents and clinicians are completing the cognitive interviews and interacting with the TELL Tool and/or eBook. The information we obtain from the Cognitive Interviews and from the Interviewer Summary Form will allow us to make final revisions and improvements to the TELL Tool, eBook, and/or the study protocol in Year 2.

Measures

Primary Outcome

*****Survey on Actual Parental Disclosure.** This 6-item survey is an accepted method for obtaining meaningful information about actual DR parent's disclosure about the donor-conception origins to their child(ren). Within this survey, we will use the question "*Have you told your child or one or more of your children about their donor conception?*" [Response options: Yes or No] to establish whether DR parents have/have not disclosed to their child(ren).

Sample Size

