We anticipate recruiting 75 DR parents in order to retain 60 DR parents through follow-up, conservatively assuming 80% retention given the 86% retention rate in our 12-year pilot study. The planned recruitment of 75 DR parent participants will allow point estimates and confidence intervals of our feasibility metrics (e.g., recruitment and retention) and means and standard deviations by treatment arm in outcome measures.

For the cognitive interview sample of 20 participants, we will include a sub-sample of 10 DR parents from our larger sample of DR parents, based on their 1) responses to the *Acceptability of the TELL Tool or eBook Survey* (e.g., participants who give detailed responses) and 2) in consideration of the maximum variation sampling plan (e.g., DR parent's gamete donation type, parent type, age category of the children to be told, and the 10% minority DR parent composition requirement). Maximum variation sampling will also be used to obtain the sample of 10 practicing clinicians for the cognitive interviews to allow for representation of nurses, physicians, psychologists, and social workers. The sample size for the 20 cognitive interviews (10 DR parents/10 clinicians) is consistent with International expert recommendations for decision aid development; other investigators that have developed decision aids; the needs of the study, and the acceptability evaluation and cognitive interviews used successfully in the development of the CHOICES intervention, a similar reproductive intervention.

Statistical Analysis Plan

We will emphasize descriptive statistics such as means, standard deviations, effect sizes, medians, interquartile ranges, frequencies, and percentages to demonstrate the feasibility of recruitment, adherence, retention, acceptability, and treatment effects of change in outcomes between the TELL Tool and the attention control eBook groups. Confidence intervals will be used to estimate a plausible range of values for these estimates.

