Because our data analysis plan includes looking ahead to a full efficacy trial where we will use a mixed-effect model for repeated measures (MMRM), which is recommended for primary analysis of clinical trials with continuous endpoints using an intent-to-treat approach. We have considered the data analysis needed for our future efficacy trial in this proposed study. Noteworthy, the MMRM model can accommodate correlations due to dyad respondents and repeated measurements and handles missing outcomes with a maximum likelihood method appropriate when data are assumed to be missing at random. We will examine the planned model using our pilot data to assess if the statistical plan will need modification.

We will examine the extent of missing data and determine correlates of missingness through associations with our other measures and through our qualitative interviews. Including predictors of missing data will support the missing at random assumption in our future efficacy trial. Other goals of quantitative analyses will be to examine measurement scale psychometric properties, including adequate variability and ability to detect change. We will examine the pattern of outcomes over time to identify the optimal endpoint for outcome assessment. Purported mediators will be examined for change over time and change scores of mediators and outcomes will be correlated. In addition, we will explore our pilot results for trends to identify potential moderators such as age group of the child. These analyses will further inform future improvement of the TELL Tool.

Primary Purpose

The primary purpose of this pilot trial is feasibility because our objective is to examine the feasibility, acceptability, and preliminary effects of the TELL Tool intervention in a pilot randomized-controlled feasibility trial.

STATISTICAL DESIGN AND POWER

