In this mixed-method study, we will use a 1:1 parallel groups randomized-controlled trial with targeted recruitment of 60 DR parents. A parent dyad will count as 1 DR parent as does a single parent or a family with multiple donor-conceived children. In view of our prior research with DR parents, we expect about 90% of the 60 DR parent participants ($n = 54$) will be dyadic DR parents (108 individuals) and 6 individuals will comprise 6 “single” DR parents in the sample for a total of 114 DR parent participants. Because this is a pilot randomized-controlled feasibility trial, the focus of the analyses will be on the feasibility of study procedures, however, our planned enrollment of 75 DR parent participants will allow point estimates and confidence intervals of our feasibility metrics (e.g., recruitment and retention) and means and standard deviations by the intervention (TELL Tool) and attention control (eBook) groups in our primary outcome measure.

04-06-2023 Update

A reliance agreement was obtained between the IRBs from the University of Illinois Chicago and the University of Michigan as [name] is now [name] at the University of Illinois Chicago and also a Professor at the University of Michigan.

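### The mediator analysis correlates change scores with no arm term stated; if the arms are pooled, the correlation can reflect the tool's effect on both variables rather than a link between them

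*Combined protocol and SAP*

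**What the plan says.** The whole mediator analysis is one sentence in the Statistical Analysis Plan section: "Purported mediators will be examined for change over time and change scores of mediators and outcomes will be correlated". The section does not name the mediators, say whether the correlation is pooled or within arm, or give a model or an indirect-effect estimate. The mixed model described there is for outcomes in the future efficacy trial, and the between-arm descriptive comparisons promised at the start of the section are also for outcomes.

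The stated use of this and the neighbouring exploratory analyses is: "These analyses will further inform future improvement of the TELL Tool".

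The relevant design facts are these:

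- **Allocation** (Statistical Design and Power): "we will use a 1:1 parallel groups randomized-controlled trial with targeted recruitment of 60 DR parents".
- **Numbers** (Sample Size): "We anticipate recruiting 75 DR parents in order to retain 60 DR parents through follow-up, conservatively assuming 80% retention".
- **Individuals behind the 60 units** (Statistical Design and Power): "6 individuals will comprise 6 “single” DR parents in the sample for a total of 114 DR parent participants".
- **Scales** (Delivery of Interventions): an immediate post-test survey "measuring our (preliminary) outcomes for intention, competence, and anxiety about disclosing the donor conception to their children". The text calls these outcomes, not mediators.
- **Primary outcome** (Measures): a single disclosure item, "Response options: Yes or No] to establish whether DR parents have/have not disclosed to their child(ren".

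**The concern.** A mediator is worth studying if the tool moves it and if it is in turn related to the outcome. The planned sentence does not isolate either link.

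First, change over time within participants does not show that the tool moved the mediator. Both arms may change; the between-arm difference is what carries the tool's effect.

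Second, in a two-arm trial any two variables that the tool shifts will correlate when the arms are pooled, because both means differ by arm. That correlation exists even if, among parents given the same material, the mediator says nothing about the outcome. If the tool moves the two in opposite directions, for example lowering anxiety and raising intention, the spurious correlation is negative.

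At stake is a development decision: which mechanisms to strengthen in the tool. A false lead at that step could carry into the later trial. The feasibility results are not affected.

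**Working it through.** **The plan's own figures.** 60 / 0.80 = 75 recruited, as stated. 0.90 × 60 = 54 dyads, and 2 × 54 + 6 = 114 individuals, as stated. At 1:1 allocation, 60 retained families are 30 per arm. No figure is given for the mediator analysis, so the effect sizes, disclosure rates and 5% two-sided threshold below are assumptions, shown over a range.

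**Expected pooled correlation.** Let the tool shift the mediator by d_M and the outcome by d_Y, in within-arm SD units, with zero within-arm correlation. With equal arms the arm indicator has variance 1/4, so the pooled covariance is d_M·d_Y/4 and the pooled variances are 1 + d²/4:

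r = (d_M·d_Y/4) / √[(1 + d_M²/4)(1 + d_Y²/4)]

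For equal effects this reduces to d²/(4 + d²):

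- d = 0.5: 0.25/4.25 = 0.059
- d = 0.8: 0.64/4.64 = 0.138
- d = 1.0: 1/5 = 0.200

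For unequal effects of 1.0 and 0.5: 0.125/√(1.25 × 1.0625) = 0.108.

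**How often a 5% test would flag it.** Simulation of 20,000 trials per scenario, with no within-arm relation:

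| Effects (SD) | Expected r | 60 units, pooled | 74 units, pooled | 114 units, pooled | Arm-adjusted, all sizes |
|---|---|---|---|---|---|
| 0.2, 0.2 | 0.01 | 5% | 5% | 5% | about 5% |
| 0.5, 0.5 | 0.06 | 7% | 8% | 9% | about 5% |
| 0.8, 0.8 | 0.14 | about 18% | 22% | 32% | about 5% |
| 1.0, 1.0 | 0.20 | 34% | 41% | 58% | about 5% |
| 1.2, 1.2 | 0.27 | 56% | 65% | 84% | about 5% |
| 1.0, 0.5 | 0.11 | 13% | 15% | 21% | about 5% |

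The mean arm-adjusted r is 0.00 throughout. The 74 column stands for nearly all 75 recruits in two equal arms. The 114 column treats individuals as independent and ignores dyads, so it shows only what a naive individual-level analysis would do.

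**Where a flag becomes more likely than not.** With 58 degrees of freedom the critical t is 2.00, so the critical r is 2.00/√(2.00² + 58) = 0.254. Setting d²/(4 + d²) = 0.254 gives d = √(4 × 0.254/0.746) = 1.17. Both effects would have to be about 1.2 SD.

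**Binary disclosure, 60 units, mediator effect 0.8 SD.** Disclosure of 10% against 30% gives pooled r = 0.09, flagged in 11% of trials; 10% against 50% gives r = 0.16, flagged in 24%. Arm-adjusted: r = 0.00 and about 5%.

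**Scale of the bias.** At 60 families the 95% interval around a zero arm-adjusted correlation is about ±tanh(1.96/√56) = ±0.26. A bias of 0.06 is small beside that; 0.20 is not. In each arm of 30 taken alone the interval is ±tanh(1.96/√27) = ±0.36.

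**The case against.** Four objections have force.

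**Pooling is not stated.** A reader might infer that the plan has decided to pool the arms. It has not: it is silent. Pooling is the natural literal reading of a sentence with no mention of arm, but this is an omission, not a declared choice.

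**No test or mediation claim is planned.** The section emphasizes description and confidence intervals, calls the mediators purported, and places the correlation among secondary goals of a trial whose primary purpose is feasibility. The flag rates are a way to express the size of the bias, not a rule in the plan. The Delivery of Interventions section also assigns the final revisions of the tool to the cognitive interviews and the interviewer's field notes, so the correlation is one input among several.

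**The bias is modest unless effects are large.** A reader might infer that a tool that moves both variables will look mediated. Under the assumed effects up to 1.0 SD, most trials of 60 families would not be flagged.

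**Change scores need a baseline.** No pre-test administration of the Outcomes Survey is described, so the analysis may not be possible as written. This does not remove the point. Eligibility requires that parents have not yet told, so later disclosure is already a change from a known start. If a baseline is added, the planned correlation becomes possible; if post-test scores are correlated instead, the same formula applies.

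It is also true that the between-arm comparison of outcomes would partly cover the first link if the mediators turn out to be intention, competence or anxiety. Since no mediators are named, that cannot be relied on.

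**Conclusion.** The point holds as a gap with a biased default. As written, the mediator analysis states no arm term or within-arm estimate. If the arms are pooled, the correlation mixes the tool's effect on each variable with the association between them. The bias in r runs from about 0.06 at assumed effects of 0.5 SD, through 0.14 at 0.8 SD, to 0.20 at 1.0 SD. It vanishes when arm is conditioned on. These figures assume equal arms, zero within-arm correlation and 60 independent families; none of the effect sizes is in the documents.

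The consequence is a possibly misleading choice of mediators for improving the tool. A reader might go further and infer a wrong trial conclusion or a false claim of mediation; the documents support neither, because the analysis is exploratory and no such claim is planned. The change is worth making because it is nearly free, not because harm is likely.

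**What to change.** Replace the mediator sentence in the Statistical Analysis Plan section with wording such as:

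> For each named mediator we will report (1) the between-arm difference and (2) its association with the outcome, adjusted for arm or estimated within arm, each with a 95% confidence interval and allowing for dyads. These analyses are exploratory and do not establish mediation.

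Some details should be settled with it:

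- **Name the mediators**, and say which measures are outcomes in this analysis.
- **Prefer adjustment for arm** as the main estimate. Separate estimates from 30 families per arm are less precise and serve as a supplement.
- **Respect time order where possible**: relate the immediate post-test mediator to later disclosure. Both surveys are already scheduled.
- **Do not commit to one regression model for disclosure.** If control disclosure were 5% (assumed), the chance of no events among 30 control families would be 0.95^30 = 21%; at 10% it would be 0.90^30 = 4%. A logistic model could then be unstable, so a descriptive alternative should be allowed.
- **Adjust for a baseline mediator score only if one is collected.** None is described now, and adding one would be new data collection.
- **Keep the caveat on mediation.** Adjusting for arm does not remove confounding between mediator and outcome, because the mediator is not randomized.

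The cost is one degree of freedom for arm and slightly more analysis. No change to recruitment or follow-up is needed.

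### The recruitment target is given once as 60 and three times as 75, and one label is used for both families and individuals

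*Combined protocol and SAP*

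**What the plan says.** The number to be recruited or enrolled is stated four times, all in current text.

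- Sample Size, first sentence: "We anticipate recruiting 75 DR parents in order to retain 60 DR parents through follow-up". The basis offered for the step from 75 to 60 is this: "conservatively assuming 80% retention given the 86% retention rate in our 12-year pilot study".
- Sample Size, second sentence: "The planned recruitment of 75 DR parent participants will allow point estimates and confidence intervals of our feasibility metrics".
- Statistical Design and Power, first sentence: "parallel groups randomized-controlled trial with targeted recruitment of 60 DR parents".
- Statistical Design and Power, last sentence of the same paragraph: "our planned enrollment of 75 DR parent participants will allow point estimates and confidence intervals of our feasibility metrics".

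Only the first sentence of Sample Size says what 60 is (the number retained) and how it relates to 75. The closing sentence of Statistical Design and Power gives 75 enrolled and says nothing about retention.

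On the unit, Statistical Design and Power sets a rule: "A parent dyad will count as 1 DR parent as does a single parent or a family with multiple donor-conceived children". The next sentence begins "we expect about 90% of the 60 DR parent participants", which under that rule means 60 families. It ends with "DR parents in the sample for a total of 114 DR parent participants", where the same noun now means individual people.

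**The concern.** The trial's stated primary purpose is feasibility. The Statistical Analysis Plan section lists recruitment, adherence, retention and acceptability among the things to be described, and the sample-size statements give recruitment and retention as examples of feasibility metrics. A recruitment target given as two different numbers leaves the reference point for the recruitment result open. If recruitment is reported as a share of target, 60 enrolled families would be 60/60 = 100% of one figure and 60/75 = 80% of the other. A team working to the lower figure would need every family to stay in the study to finish with 60.

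The double use of the label adds to this. Someone who meets 60, 75 and 114 under one noun, in two consecutive sentences, has to work out which are families and which are people, and which of them is the denominator for retention.

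**Working it through.** **Inputs.** From Sample Size: 75 recruited, 60 retained, 80% retention assumed, 86% cited from earlier work. From Statistical Design and Power: 60 as the recruitment figure, 75 as enrolment, a dyad counted as 1, 90% dyads among the 60, and 114 in total.

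**Step 1. Reproduce the plan's own figures.**
- Recruitment needed to retain 60 at 80%: 60 / 0.80 = 75. This matches.
- Individuals in 60 families: 0.90 × 60 = 54 dyads; 54 × 2 = 108; 60 − 54 = 6 single parents; 108 + 6 = 114. This matches.

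**Step 2. Take each recruitment figure in turn.**

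| Recruited | Retained at 80% | Retained at 86% |
|---|---|---|
| 75 | 75 × 0.80 = 60 | 75 × 0.86 = 64.5 |
| 60 | 60 × 0.80 = 48 | 60 × 0.86 = 51.6 |

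Recruiting 60 does not retain 60 at either rate. Retaining 60 needs 75 at 80%, or 60 / 0.86 = 69.8, so 70, at 86%. Only 75 agrees with the plan's stated assumption.

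**Step 3. Ask whether the counting unit explains the gap.** By the plan's figures there are 114 / 60 = 1.9 individuals per family. Sixty families are therefore 114 individuals, not 75, and 75 individuals would be 75 / 1.9, or about 39 families, not 60. Families versus individuals does not reconcile 60 with 75.

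**Step 4. Place the 114.** It belongs to 60 families. If the 90% dyad share also held at enrolment (an assumption; the plan applies it only to the 60), 75 families would include 67 or 68 dyads, giving 67 × 2 + 8 = 142 or 68 × 2 + 7 = 143 individuals. The plan gives no count of individuals at enrolment.

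**Step 5. Size the effect on precision.** The Wilson 95% half-width for a proportion p is z·√(p(1−p)/n + z²/(4n²)) / (1 + z²/n), with z = 1.96 and retention p = 0.80.
- n = 75 (60/75): 1.96 × √(0.002133 + 0.000171) / 1.0512 = 0.089; interval 69.6% to 87.5%.
- n = 60 (48/60): 1.96 × √(0.002667 + 0.000267) / 1.0640 = 0.100; interval 68.2% to 88.2%.

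The difference is about one percentage point in half-width.

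**The case against.** The best defence is that a careful reader can settle the matter. Three of the four statements say 75, one of them in the same paragraph as the 60; the section devoted to sample size is unambiguous; and only 75 fits the stated retention. A team would have to overlook all of that to recruit to 60. The documents do not define recruitment as a percentage of target and set no progression threshold on it, so the 100% versus 80% contrast depends on a form of reporting the plan does not specify. On the label, the plan gives the counting rule and marks the 108 and the 6 as individuals before adding them, so nobody will misread that sum. It might also be said that the word targeted in the 60 sentence describes the kind of recruitment rather than a goal.

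Most of this stands, and it limits the consequence. It does not remove the conflict. Even if targeted describes the method, the number attached to recruitment is still 60, against 75 at the end of the paragraph. That the answer can be inferred is a reason to expect an easy correction, not a reason to leave two numbers in the plan.

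Stronger readings are tempting. A reader might infer that the sample-size arithmetic is wrong; it is not, since both calculations reproduce exactly. A reader might infer that the trial is underpowered or loses much precision; the plan is based on estimation and states no power, and the loss would be about one point. A reader might also infer from the loose label that the analysis of partners within a dyad is invalid. The 60/75 conflict does not show that. The Statistical Analysis Plan section already acknowledges correlation between dyad respondents, and how a dyad counts as retained or enters the descriptive intervals is a separate question.

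**Conclusion.** The inconsistency is real and should be corrected. One statement gives recruitment as 60 and three give 75. Only 75 is consistent with the assumed 80% retention, so the 60 is most plausibly the retained number carrying the wrong label. That is an inference, and it rests on the single sentence in Sample Size that defines 60 as retained; the sponsor must confirm it. The term for participants is also applied to 60 families, 114 individuals and 75 families, against the plan's own counting rule.

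This is more than a clerical slip, because a feasibility trial relies on its recruitment target. The size is modest: 48 rather than 60 families retained if the lower figure were followed at 80% retention, and a half-width of 10.0 rather than 8.9 points on the retention estimate. It is an inconsistency of stated figures and terms, not an error of calculation or a flaw in the design.

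**What to change.** The sponsor should confirm which recruitment figure is intended. If it is 75, restate the opening of Statistical Design and Power along these lines: *The trial will aim to recruit 75 DR parent families so that 60 are retained; of those 60, about 54 are expected to be dyads and 6 single parents, making 114 individuals.* Use *family* for the counted unit and *individual* for partners throughout, and report recruitment against 75 families and retention per family.

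The cost is one reworded sentence and consistent terms. If 75 is confirmed, nothing changes in the design, the sample size or data collection. If the sponsor instead means 60, the Sample Size section and the closing sentence of Statistical Design and Power must be rewritten and the expected number retained restated.
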